# 7.1.2. Temporary Discontinuation from Study Treatment

Not applicable.

# 7.1.3. Discontinuation of Inadvertently Enrolled Patients

If the sponsor or investigator identifies a patient who did not meet enrollment criteria and was inadvertently enrolled, a discussion must occur between the sponsor CRP/CRS and the investigator to determine if the patient may continue in the study. If both agree it is medically appropriate to continue, the investigator must obtain documented approval from the sponsor

CRP/CRS to allow the inadvertently enrolled patient to continue in the study with or without treatment with investigational product.

## 7.1.4. Permanent Discontinuation from the Study

Some possible reasons that may lead to permanent discontinuation include:

- Enrollment in any other clinical trial involving an investigational product or enrollment in any other type of medical research judged not to be scientifically or medically compatible with this study
- Participation in the study needs to be stopped for medical, safety, regulatory, or other reasons consistent with applicable laws, regulations, and good clinical practice (GCP)
- Investigator Decision
  - o the investigator decides that the patient should be discontinued from the study
  - o if the patient, for any reason, requires treatment with another therapeutic agent that has been demonstrated to be effective for the study indication (prevention of migraine) during Study Period III, discontinuation from the study occurs prior to introduction of the new agent
- Subject Decision
  - o the patient asks to be withdrawn from the study

Patients who discontinue the study early will have end-of-study (early termination) procedures performed as shown in the Schedule of Activities (Appendix 2) and are requested to proceed into the post-treatment phase.

# 7.1.5. Patients Lost to Follow-Up

A patient will be considered lost to follow-up if he or she repeatedly fails to return for scheduled visits and is unable to be contacted by the study site. Site personnel are expected to make diligent attempts to contact patients who fail to return for a scheduled visit or were otherwise unable to be followed up by the site.

# 8. Study Assessments and Procedures

Appendix 2 lists the Schedule of Activities, with the study procedures and their timing (including tolerance limits for timing).

Appendix 3 lists the laboratory tests that will be performed for this study.

Appendix 4 lists the tests that may be obtained in the event of a treatment-emergent hepatic abnormality.

Unless otherwise stated in the subsections below, all samples collected for specified laboratory tests will be destroyed within 60 days of receipt of confirmed test results. Certain samples may be retained for a longer period, if necessary, to comply with applicable laws, regulations, or laboratory certification standards.

# 8.1. Efficacy Assessments

# 8.1.1. Primary Efficacy Assessments

ePRO Diary: Patients will be asked to use an ePRO device (starting at Visit 2) to record headache symptoms, duration, and severity. The device also will be used to collect the name and dose of concomitant medications used for the acute treatment of migraine, and the use of other pain medications.

# 8.1.2. Secondary Efficacy Assessments

# 8.1.2.1. Patient Global Impression of Severity

The Patient Global Impression of Severity (PGI-S) scale (Guy 1976) is a patient-rated instrument that measures baseline illness severity. The PGI-S includes a range of possible responses, from 1 ("normal, not at all ill") to 7 ("extremely ill").

# 8.1.2.2. Patient Global Impression of Improvement

The Patient Global Impression of Improvement (PGI-I) scale (Guy 1976) is a patient-rated instrument that measures improvement of the patient's symptoms. It is a 7-point scale in which a score of 1 indicates the patient is "very much better," a score of 4 indicates the patient has experienced "no change," and a score of 7 indicates the patient is "very much worse."

# 8.1.3. Appropriateness of Assessments

All efficacy and safety assessments have been well documented and are generally regarded as reliable, accurate, and relevant in this patient population. This includes health outcomes measures considered to be appropriate for evaluating changes in quality of life, global functioning, and disability (Section 8.9).

#### 8.2. Adverse Events

Investigators are responsible for monitoring the safety of patients who have entered this study and for alerting Lilly or its designee to any event that seems unusual, even if this event may be considered an unanticipated benefit to the patient.

The investigator is responsible for the appropriate medical care of patients during the study.

Investigators must document their review of each laboratory safety report.

The investigator remains responsible for following, through an appropriate health care option, AEs that are serious or otherwise medically important, considered related to the investigational product or the study, or that caused the patient to discontinue the investigational product before completing the study. The patient should be followed until the event resolves, stabilizes with appropriate diagnostic evaluation, or is reasonably explained. The frequency of follow-up evaluations of the AE is left to the discretion of the investigator.

Lack of drug effect is not an AE in clinical studies, because the purpose of the clinical study is to establish treatment effect.

After the ICF is signed, study site personnel will record via eCRF the occurrence and nature of each patient's pre-existing condition(s), including clinically significant signs and symptoms of the disease under treatment in the study. In addition, site personnel will record via eCRF any change in the condition(s) and any new condition(s) as AEs. Investigators should record their assessment of the potential relatedness of each AE to protocol procedure or investigational product via eCRF.

The investigator will decide whether he or she interprets the observed AEs as reasonably possibly related to migraine headache, to the investigational product, study device, study procedure, or other concomitant treatment or pathologies.

The investigator will answer yes/no when making this assessment.

Planned surgeries and nonsurgical interventions should not be reported as AEs unless the underlying medical condition has worsened during the course of the study.

If a patient's investigational product is discontinued as a result of an AE, study site personnel must report this to Lilly or its designee via eCRF, clarifying if possible, the circumstances leading to discontinuations of treatment.

#### 8.2.1. Serious Adverse Events

An SAE is any AE from this study that results in one of the following outcomes:

- death
- initial or prolonged inpatient hospitalization
- a life-threatening experience (that is, immediate risk of dying)
- persistent or significant disability/incapacity

- congenital anomaly/birth defect
- considered significant by the investigator for any other reason: important medical events that may not result in death, be life-threatening, or require hospitalization may be considered serious, based upon appropriate medical judgment
- when a condition related to the investigational device (for example, prefilled syringe) necessitates medical or surgical intervention to preclude either permanent impairment of a body function or permanent damage to a body structure, the serious outcome of "required intervention" will be assigned

Although all AEs after signing the ICF are recorded in the eCRF, SAE reporting begins after the patient has signed the ICF and has received investigational product. However, if an SAE occurs after signing the ICF, but prior to receiving investigational product, it needs to be reported ONLY if it is considered reasonably possibly related to study procedure.

Study site personnel must alert Lilly or its designee of any SAE within 24 hours of investigator awareness of the event via a sponsor-approved method. If alerts are issued via telephone, they are to be immediately followed with official notification on study-specific SAE forms. This 24-hour notification requirement refers to the initial SAE information and all follow-up SAE information.

Pregnancy (during maternal or paternal exposure to investigational product) does not meet the definition of an AE. However, to fulfill regulatory requirements, any pregnancy that occurs during the study, including those in which conception occurred within 5 months after last administration of investigational product, should be reported using the SAE process to collect data on the outcome for both mother and fetus.

Investigators are not obligated to actively seek AEs or SAEs in patients once they have discontinued and/or completed the study (the patient summary eCRF has been completed). However, if the investigator learns of any SAE, including a death, at any time after a patient has been discharged from the study, and he/she considers the event reasonably possibly related to the study treatment or study participation, the investigator must promptly notify Lilly.

#### 8.2.1.1. Suspected Unexpected Serious Adverse Reactions

Suspected unexpected serious adverse reactions (SUSARs) are serious events that are not listed in the IB and that the investigator identifies as related to investigational product or procedure. United States 21 CFR 312.32 and European Union Clinical Trial Directive 2001/20/EC and the associated detailed guidance or national regulatory requirements in participating countries require the reporting of SUSARs. Lilly has procedures that will be followed for the recording and expedited reporting of SUSARs that are consistent with global regulations and the associated detailed guidance.

# 8.2.1.2. Adverse Event Monitoring with a Systematic Questionnaire

Suicidality will be assessed as required by the US Food and Drug Administration's Division of Neurology for use in clinical trials involving all drugs for neurological indications. Before administering the C-SSRS) [Posner et al. 2011]), study site personnel will question the patient

about any change in the pre-existing condition(s) and the occurrence and nature of any AEs. Nonserious AEs obtained through the questionnaire are recorded and analyzed separately. Only *serious* AEs and AEs leading to discontinuation elicited through the C-SSRS are to be recorded as AEs via eCRF. Serious adverse events must be reported to Lilly or its designee within 24 hours as SAEs. Any suicidal behavior, or suicidal ideation per items 4 or 5 (active suicidal ideation with some intent to act, either without specific plan or with specific plan and intent) would prompt referral of the patient to a mental health professional.

# 8.2.2. Complaint Handling

Lilly collects product complaints on investigational products and drug delivery systems used in clinical studies in order to ensure the safety of study participants, monitor quality, and to facilitate process and product improvements.

Patients will be instructed to contact the investigator as soon as possible if he or she has a complaint or problem with the investigational product (or drug delivery system such as a prefilled syringe) so that the situation can be assessed.

### 8.3. Treatment of Overdose

No data are available at this stage of development.

# 8.4. Safety Assessments

# 8.4.1. Electrocardiograms

For each patient, a single, 12-lead digital ECG will be collected at the visits shown in the Schedule of Activities (Appendix 2). Electrocardiograms will have a central overread and should be recorded according to the study-specific recommendations included in the ECG manual.

Any clinically significant findings from ECGs that result in a diagnosis should be reported to Lilly or its designee as an AE via eCRF.

# 8.4.2. Vital Signs

Vital signs will include body temperature, blood pressure, and pulse. Blood pressure and pulse will be measured in triplicate in the sitting position prior to blood draws and study drug administration (see Study Schedule [Appendix 2]).

Any clinically significant findings from vital signs measurement that result in a diagnosis should be reported to Lilly or its designee as an AE via eCRF.

# 8.4.3. Laboratory Tests

For each patient, laboratory tests detailed in Appendix 3 should be conducted according to the Schedule of Activities (Appendix 2).

Any clinically significant findings from laboratory tests that result in a diagnosis should be reported to Lilly or its designee as an AE via eCRF.

In addition, an immunogenicity plasma sample will be collected, when possible, for any patient who experiences a potential systemic allergic/hypersensitivity reaction during the study as judged by the investigator. This immunogenicity plasma sample should be collected immediately or as soon as possible, taking into consideration the availability and wellbeing of the patient. Exact date and time of the sample should be recorded on the laboratory requisition form.

#### 8.4.4. Other Tests

Not applicable.

# 8.4.5. Safety Monitoring

Investigators are responsible for monitoring individual patient safety throughout the trial. If a study patient/subject experiences elevated ALT ≥3X ULN, ALP ≥2X ULN, or elevated TBL ≥2X ULN, clinical and laboratory monitoring should be initiated by the investigator. Details for hepatic monitoring depend upon the severity and persistence of observed laboratory test abnormalities. To ensure patient/subject safety and comply with regulatory guidance, the investigator is to consult with the Lilly CRP/CRS regarding collection of specific recommended clinical information and follow-up laboratory tests. See Appendix 4.

Neurological examinations will be conducted at screening, Month 3 and Month 6 of treatment, as well as at the final visit of the follow-up period or early termination visit in order to assess for any signs of pre-existing or treatment-emergent neurological abnormalities such as stroke or other cerebrovascular events. If a study patient experiences signs of a cerebrovascular event, appropriate follow-up and clinical management should be conducted by the investigator, and the Lilly CRP/CRS should be consulted regarding collection of further clinical information and follow-up testing.

Lilly will periodically review evolving aggregate safety data within the study by appropriate blinded methods. In addition, safety data for the trial will also be reviewed periodically by an independent Data Monitoring Committee (DMC; an advisory group for this study formed to protect the integrity of data; refer to Interim Analyses section [Section 9.8]). In the event that safety monitoring uncovers an issue that needs to be addressed by unblinding at the group level, members of the DMC can request additional analyses of the safety data.

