# 7.1. Discontinuation from Study Treatment

# 7.1.1. Permanent Discontinuation from Study Treatment

Discontinuation of the investigational product is required in cases of pregnancy.

Discontinuation of the investigational product for abnormal liver tests is required when a patient meets one of the following conditions and the event is at least possibly related to study drug:

- ALT or aspartate aminotransferase (AST) >8X ULN
- ALT or AST >5X ULN for more than 2 weeks
- ALT or AST >3X ULN and TBL >2X ULN or prothrombin time >1.5X ULN
- ALT or AST >3X ULN with the appearance of fatigue, nausea, vomiting, right upper-quadrant pain or tenderness, fever, rash, and/or eosinophilia (>5%)
- ALP >3X ULN
- ALP >2.5X ULN and TBL >2X ULN
- ALP >2.5X ULN with the appearance of fatigue, nausea, vomiting, right quadrant pain or tenderness, fever, rash, and/or eosinophilia (>5%)

Discontinuation of investigational product also is required in the following cases, if the event is at least possibly related to study drug:

- Serious allergic reaction to study drug
- Serious injection-site reaction
- Serious event of suicidality or depression
- Serious cerebrovascular event.

Patients who discontinue the investigational product early will have end-of-therapy (early termination) procedures performed as shown in the Schedule of Activities (Appendix 2) and are requested to proceed into the post-treatment phase.

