PGI-S			X		X	X	X	X		X		X		X	X
PGI-I					X	X	X	X		X		X			X
C-SSRS/SHSF, SHFU m	X	X	X		X	X	X	X		X		X	X	X	X

Abbreviations: AE = adverse event; CGRP = Calcitonin-gene related peptide; C-SSRS = Columbia-Suicide Severity Rating Scale; ECG = electrocardiogram; ePRO = electronic patient reported outcomes; ET = early termination; FSH = follicle stimulating hormone; HDL = High-density lipoprotein; MIDAS = Migraine Disability Assessment test; MSQ (v2.1) = Migraine Specific Quality of Life Questionnaire; PGI-I = Patient Global Impression of Improvement; PGI-S = Patient Global Impression of Severity; PK = pharmacokinetics; RNA = ribonucleic acid; SHSF = Self-harm supplement form; SHFU = Self-harm follow-up form.

Note: Selected tests may be obtained in the event of a treatment-emergent hepatic abnormality and may be required in follow-up with patients in consultation with the Lilly, or its designee, clinical research physician. See Appendix 4 for more details regarding specific hepatic monitoring tests. If the patient has discontinued the trial and returns for hepatic follow-up, the site should use the 800 series as the visit designation.

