# Appendix 4. Hepatic Monitoring Tests for Treatment-Emergent Abnormality

Selected tests may be obtained in the event of a treatment-emergent hepatic abnormality and may be required in follow-up with patients in consultation with the Lilly, or its designee, clinical research physician.

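### The trigger for hepatic monitoring in Protocol 8.4.5 omits AST, although the mandatory stopping rules in 7.1.1 apply to ALT or AST

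*Protocol*

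**What the plan says.** Protocol 8.4.5 (Safety Monitoring) gives the starting point for hepatic follow-up: "If a study patient/subject experiences elevated ALT ≥3X ULN, ALP ≥2X ULN, or elevated TBL ≥2X ULN, clinical and laboratory monitoring should be initiated". Once that point is reached, "the investigator is to consult with the Lilly CRP/CRS regarding collection of specific recommended clinical information and follow-up laboratory tests". The extent of monitoring is then set by how large and how lasting the abnormality is.

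Protocol 7.1.1 makes stopping treatment compulsory on listed liver limits, provided a relation to study drug is at least possible. Four of the listed conditions are written for either transaminase: above 8X ULN on its own; "ALT or AST >5X ULN for more than 2 weeks"; "ALT or AST >3X ULN and TBL >2X ULN or prothrombin time >1.5X ULN"; and above 3X with listed symptoms or eosinophilia. Section 7.1.1 itself contains no retest or consultation step.

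Other relevant text:

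- AST and creatine kinase are both in the routine chemistry panel (Appendix 3). Prothrombin time is not; it appears only in Appendix 4.
- Appendix 4 is permissive: "Selected tests may be obtained in the event of a treatment-emergent hepatic abnormality". The note to Appendix 2 adds that such tests "may be required in follow-up with patients in consultation with the Lilly, or its designee, clinical research physician". Neither names an enzyme threshold.
- Section 8.2 obliges investigators to record that they have reviewed each laboratory report and to follow related or medically important adverse events, but "The frequency of follow-up evaluations of the AE is left to the discretion of the investigator".
- Section 8.4.3 makes a laboratory finding reportable as an adverse event under a condition: "Any clinically significant findings from laboratory tests that result in a diagnosis should be reported".
- SAP 5.5.12.1.5 summarises ALT or AST at 3, 5 and 10 times ULN, which is analysis only.

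**The concern.** A compulsory stopping rule works only if something leads the site to collect the data that the rule needs. For ALT the chain is complete: a value of 3X or more starts monitoring and a conversation with the sponsor physician well before 5X is reached. For AST the stopping limits are the same, but the step that starts the chain is absent.

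At stake is a patient whose AST is between 5X and 8X ULN with nothing else abnormal. Such a patient could receive further doses before anyone establishes whether the rise has lasted more than two weeks. Two features make timing matter. Section 7.1.2 treats temporary discontinuation as not applicable, so the protocol describes no dose hold while persistence is checked. The antibody also clears slowly. Section 4.3 equates about 5 months with about 5 half-lives, so one half-life is about a month, and a dose already given cannot be withdrawn quickly.

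**Working it through.** **Step 1. Which AST rises lack a prompt.** The table applies each AST condition in 7.1.1 to a patient whose ALT is below 3X ULN and whose ALP is below 2X ULN, and asks whether the 8.4.5 trigger is also met.

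| AST finding | Effect under 7.1.1 | 8.4.5 trigger met? | What is left open |
|---|---|---|---|
| Above 8X | Stop on one value | No | Nothing; no retest is needed |
| Above 3X with listed symptoms or eosinophilia | Stop at once | No | Nothing |
| Above 3X with TBL above 2X | Stop | Yes, through TBL | Nothing |
| Above 5X to 8X, no symptoms, TBL below 2X | Stop only if it lasts more than 2 weeks | No | A second value is needed and nothing specific prompts it |
| Above 3X, no symptoms, TBL below 2X | Stop only if prothrombin time is above 1.5X | No | Prothrombin time is not a routine test |

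The fourth row is the main gap. The fifth is weaker as an AST point, because no enzyme value makes prothrombin time compulsory, ALT included.

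**Step 2. Whether the visit schedule fills the gap.** Inputs are from Appendix 2. Chemistry is scheduled at Visits 1, 3, 7, 12 and 14 and at early termination. Doses are given at Visits 3, 5, 6, 7, 8 and 10, after the other procedures of the visit.

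- First dose to first later chemistry (Visit 3 to 7): 14 + 16 + 30 + 30 = 90 days. Allowances sum to 1 + 3 + 2 + 2 = 8, giving 82 to 98 days.
- Visit 7 to the next chemistry (Visit 12): 30 + 15 + 15 + 15 + 15 = 90 days. Allowances sum to 5 × 2 = 10, giving 80 to 100 days.
- Doses after Visit 7 and before Visit 12: Visits 8 and 10, so 2 of 6. Visit 8 falls 28 to 32 days after Visit 7.
- Last dose (Visit 10) to Visit 12: 15 + 15 = 30 days, so the Visit 12 result can no longer prevent a dose.

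Visit 7 is therefore the only scheduled chemistry after the first dose that still has later doses to protect. The rule needs more than 14 days of persistence, and the next scheduled value comes at least 80 days later.

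**Step 3. Half-life.** Five half-lives leave 0.5^5 = 3.1%, a fall of 96.9%. This agrees with the roughly 97% in section 4.3 and supports a half-life of 5 / 5 = 1 month.

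No sample size, power or alpha figure enters the point.

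**The case against.** The strongest reply is that an isolated AST rise will be seen and can be followed up. Section 8.2 makes review of every laboratory report compulsory, 8.4.5 makes investigators responsible for individual safety, and Appendix 4 covers any hepatic abnormality, with AST and prothrombin time on its list. A rule that requires more than two weeks of persistence also implies a second value. All of this stands. It limits the point to a missing prompt, because these provisions are general or permissive and set no AST threshold.

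The omission may also be deliberate. Exclusion criterion 25, the deviation list in the SAP appendix and the SAP's Hy's law definition use ALT, ALP and bilirubin without AST. Those passages serve screening, deviation reporting and case definition, however, and none has to feed an AST stopping rule. The documents give no reason for leaving AST out of 8.4.5.

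A reader might go further and infer that the plan is also deficient, for both enzymes, in giving no fixed repeat interval for the two-week rule. The documents do not support that. An ALT value above 5X has already met the 3X trigger, sponsor consultation then applies, and follow-up is set case by case according to severity and persistence. A fixed instruction to retest after day 14 could even be read as postponing an earlier check for a rise past 8X, raised bilirubin or an abnormal prothrombin time.

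**Conclusion.** The point holds in a narrow form. Read literally, the 8.4.5 trigger does not match the enzymes in the mandatory rules of 7.1.1. For an isolated, symptom-free AST above 5X and up to 8X ULN, no text specifically prompts the retest on which the two-week rule depends.

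The 90-day interval (80 to 100) and the two intervening doses describe what happens if only scheduled chemistry is done. They should not be read as the protocol's intended way of judging the rule, nor as evidence that AST rises go unmonitored, since extra tests are expressly allowed.

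The conclusion assumes that the rise is first found at Visit 7, that ALT, ALP and bilirubin stay below their triggers, that a drug relation is at least possible, and that the site adds no test of its own accord. The documents give no rate for such rises, so the number of patients cannot be derived; it is expected to be very small. This is a minor safety alignment with no effect on any endpoint, analysis, alpha or power.

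**What to change.** In Protocol 8.4.5, change the transaminase trigger from ALT to ALT or AST, at 3X ULN or more. AST rises then enter the same severity-based monitoring and sponsor consultation as ALT. Prothrombin time can be considered there among the Appendix 4 tests, although the change does not make it compulsory. The change supplies the missing prompt and leaves the visit schedule as it is. If AST was left out on purpose, 8.4.5 should say so and state how the AST limits in 7.1.1 are to be judged.

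The cost is two added words and a few extra hepatic panels. Some will be for AST of muscle origin, which the creatine kinase already measured in routine chemistry helps to identify.
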